6.14.9. Histopathology

The histopathologic images will be read centrally in a blinded manner by a qualified pathologist and scoring performed using the Geboes Score and Robarts Histopathology Index (RHI) [3].

The Geboes score assigns subjects to grades 0, 1, 2A, 2B, 3, 4 and 5 according to seven histological features: structural (architectural change), chronic inflammatory infiltrate, lamina

propria eosinophils, lamina propria neutrophils, neutrophils in epithelium, crypt destruction and erosion or ulceration [3].

In practice, the highest grade in which there is evidence of disease is assigned. For example if <50% crypts involved (3.2) is checked and Crypt destruction is noted as 'none' (4.0) and Erosion or ulceration is 'No erosion, ulceration ,or granulation tissue' (5.0), the subject will be assigned a score or grade of 3. For scoring, a subject with either abnormalities in lamina propria eosinophils or lamina propria neutrophils will be assigned a score or grade of 2.

The Robarts Histopathology Index is based on the chronic inflammatory infiltrate, lamina propria neutrophils, neutrophils in epithelium, and erosion ulceration components of the Geboes score. As reported in Mosli et al, the RHI is calculated as:

$$\begin{aligned} \text{RHI} = & 1 \times \text{chronic inflammatory infiltrate level (4 levels)} \\ & + 2 \times \text{lamina propria neutrophils (4 levels)} \\ & + 3 \times \text{neutrophils in epithelium (4 levels)} \\ & + 5 \times \text{erosion or ulceration (4 levels after combining Geboes 5.1 and 5.2).} \end{aligned}$$

The total score ranges from 0 (no disease activity) to 33 (severe disease activity).

The following proposed definition for histologic remission will be used for the purpose of analyses and interpretation in this study:

- **Proposed definition: Histologic remission**, defined as Geboes histological subscores of 0 for parameters:
 - 2B (neutrophils in lamina propria), and
 - 3 (neutrophils in epithelium), and
 - 5 (erosion or ulceration)

The following three additional definitions are also presented for exploratory purposes only:

- **Exploratory definition 1: Histologic remission**, defined as Geboes histological subscores of 0 for parameters:
 - 2B (neutrophils in lamina propria), and
 - 3 (neutrophils in epithelium), and
 - 5 (erosion or ulceration)

and

 - 0 (structural [architectural change]) – no worse than baseline.
- **Exploratory definition 2: Histologic remission**, defined as Geboes histological subscores of 0 for parameters:
 - 2B (neutrophils in lamina propria) and
 - 3 (neutrophils in epithelium), and
 - 4 (crypt destruction), and
 - 5 (erosion or ulceration)

- **Exploratory definition 3: Histologic remission**, defined as Geboes histological subscores of 0 for parameters:
 - 2B (neutrophils in lamina propria)
 - 3 (neutrophils in epithelium), and
 - 4 (crypt destruction), and
 - 5 (erosion or ulceration)**and**
 - 0 (structural [architectural change]) – no worse than baseline.

Summary for the ITT population by treatment arm will be presented for each timepoint a colon biopsy was performed. Also, the change from baseline at Week 12 of the induction dosing period will be presented by treatment arm.

Subgroup summaries by previous biologics exposure, by baseline severity and any other clinically significant baseline stratification may be performed.

Two sample unpaired t-test will be employed to analyze the mean difference at Week 12 and Week 52 between each active treatment arm and placebo for each scoring method. The 95% confidence interval for the mean difference will be obtained. Similar analysis results will be presented for the previous biologics exposure subgroups.

6.15. The proportion of subjects with a Histologic Remission at week 12 and week 52 will be presented and analysed as per the methodology described in section 6.1.Subgroup Analyses

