Study Week (W)	W12- W13	W16	W20	W24	W28	W32	W36	W40	W44	W48	W52	W56	W60
Day (D)	D85-92	D113 ± 7d	D141 ± 7d	D169 ± 7d	D197 ± 7d	D225 ± 7d	D253 ± 7d	D281 ± 7d	D309 ± 7d	D337 ± 7d	D365 ± 7d	D393 ± 7d	D421 ± 7d
Randomization	X ^o												
Physical examination ^b and weight		X	X	X	X	X	X	X	X	X	X	X	X
Concomitant medications	X	X	X	X	X	X	X	X	X	X	X	X	X
Vital signs (BP and heart rate)	X	X	X	X	X	X	X	X	X	X	X	X	X
AEs	X	X	X	X	X	X	X	X	X	X	X	X	X
Dosing ^f	X	X	X	X	X	X	X	X	X	X	X	X	X
Partial Mayo score (all subjects)		X	X	X	X	X	X	X	X	X		X	X
Endoscopy											X ^p		
Colon biopsy sample collection (occurs at time of endoscopy)											X ^p		
Full Mayo score (only patients who meet eligibility criteria for endoscopy will have a full Mayo score)											X		
Subject diary data review/collection		X	X	X	X	X	X	X	X	X	X	X	X
IBDQ, SF-36, and PGI-I				X		X					X		
ECG						X					X		
HBV PCR ^q (only if HBcAb+ with negative HBV PCR test at screening)				X			X			X			X
Urine pregnancy test ⁱ		X	X	X	X	X	X	X	X	X	X	X	X
Blood draws for hematology and serum chemistry		X	X	X	X	X	X	X	X	X	X	X	
NGAL and MMP-9				X							X		
LY3074828 PK samples ⁿ	X	X	X	X		X		X		X		X	
LY3074828 postdose samples	X ^r (2-10 days postdose)												
Urinalysis		X		X		X		X		X			
CRP		X	X	X	X	X	X	X	X	X	X		
Samples for exploratory biomarkers (whole blood, serum, plasma)				X							X		
Immunogenicity samples ⁿ		X		X		X		X		X		X	
Fecal sample (eg, fecal calprotectin)											X		

**Study Schedule, Protocol I6T-MC-AMAC
Maintenance Dosing and Follow-Up Periods (4 of 4)**

	Maintenance Dosing Period											Follow-Up Period			
Visit No (V)	V21	V22	V23	V24	V25	V26	V27	V28	V29	V30	V31	V801	V802	V803	V804
Study Week (W)	W64	W68	W72	W76	W80	W84	W88	W92	W96	W100	W104	W108	W112	W116	W120 ^s / EOS/ET
Day (D)	D448 ± 7d	D476 ± 7d	D504 ± 7d	D532 ± 7d	D560 ± 7d	D588 ± 7d	D616 ± 7d	D644 ± 7d	D672 ± 7d	D700 ± 7d	D728 ± 7d	D756 ± 7d	D784 ± 7d	D812 ± 7d	D840 ± 7d
Physical examination ^b and weight	X	X	X	X	X	X	X	X	X	X	X	X	X	X	X
Concomitant medications	X	X	X	X	X	X	X	X	X	X	X	X	X	X	X
Vital signs (BP and heart rate)	X	X	X	X	X	X	X	X	X	X	X	X	X	X	X
AEs	X	X	X	X	X	X	X	X	X	X	X	X	X	X	X
Dosing ^f	X	X	X	X	X	X	X	X	X	X	X				
Partial Mayo score (all subjects)	X	X	X	X	X	X	X	X	X	X	X	X	X	X	X
Subject diary data review/collection	X	X	X	X	X	X	X	X	X	X	X	X	X	X	X
IBDQ, SF-36, PGI-S, and PGI-I															X
ECG					X						X				X
HBV PCR ^a (only if HBcAb+ with negative HBV PCR test at screening)			X			X			X			X			X

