5.1. Summary of Study Design

Study I6T-MC-AMAC is a multicenter, randomized, double-blind, parallel-arm, placebo-controlled trial in which approximately 240 patients will be randomized.

Patients must have moderate or severe UC (defined as a Mayo score of 6 to 12 with an endoscopic subscore ≥ 2). Approximately two-thirds (~160) of the patients randomized to study treatment must have been exposed to at least 1 previous biologic therapy (received treatment with 1 or more agents such as tumor necrosis factor [TNF] antagonists, vedolizumab, or experimental UC biologic therapy), and approximately one-third (~80) of the patients will be naive to biologic therapy.

Screening Period: Patients will be evaluated for study eligibility ≤ 28 days before the baseline visit.

At the baseline visit, patients who fulfill the eligibility criteria will be randomized equally to 1 of 4 induction treatment arms (LY3074828 50 mg, LY3074828 200 mg, LY3074828 600 mg, and Placebo).

Induction Dosing Period (Induction Period): A 12-week induction period is designed to establish the efficacy and safety of LY3074828 administered intravenous (IV) at Weeks 0, 4, and 8. Patients will be stratified across the treatment arms on the basis of previous exposure to biologic therapy for treatment of UC. Patients who discontinue the study for any reason before the end of the induction period will complete the early study discontinuation follow-up visit.

Maintenance Dosing Period (Maintenance Period): The maintenance period is designed to explore the safety and durability of clinical responses and remissions to treatment with 200-mg LY3074828 administered subcutaneously (SC) every 4 weeks (Q4W) or every 12 weeks (Q12W). Patients defined as having clinical responses at Week 12 will continue study participation in the maintenance period up to Week 104. Patients who do not meet clinical response criteria at Week 12 will have the option to continue in a study Extension Period or discontinue from the study.

Responding patients who have received LY3074828 in the induction period will be re-randomized to 1 of 2 LY3074828 maintenance treatment arms (200 mg SC Q4W or 200 SC mg Q12W); these patients will be stratified according to their Week-12 remission status. Any responding patients in the placebo arm will remain on placebo.

After Week 52, subjects who experience worsening of UC (partial Mayo score of 7 or more) may receive rescue treatment with LY3074828 200 mg SC Q4W.

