5.3. Method of Assignment to Treatment

Patients who meet all criteria for enrollment will be randomized to treatment at the baseline visit. Assignment to treatment groups will be determined by a computer-generated random sequence using an interactive web-response system (IWRS), and then the site will be responsible for administering the treatment to the patients.

Patients will be randomized into the Induction Dosing Period at a 1:1:1:1 ratio to one of four treatment groups, each given as one IV injection:

- 600 mg LY3074828 IV Q4W: A dose of 600 mg given as an IV infusion at Weeks 0, 4, and 8.
- 200 mg LY3074828 IV TDM Q4W: A dose of 200 mg TDM given as an IV infusion at Weeks 0, 4, and 8. Dose adjustments may occur at Week 4 and 8.
- 50 mg LY3074828 IV TDM Q4W: A dose of 50 mg TDM given as an IV infusion at Weeks 0, 4, and 8. Dose adjustments may occur at Week 4 and 8.
- Placebo: A dose of placebo saline given as IV injections at Weeks 0, 4, and 8.

Patients who have clinical responses to LY3074828 (as defined in section 6.11.3.1) at the end of the Induction Dosing Period will be re-randomized to 1 of 2 maintenance LY3074828 treatment arms in the Maintenance Dosing period. This randomization will be stratified according to the patient's Week 12 remission status.

- 200 mg SC LY3074828 Q4W: A dose of 200 mg given as a SC injection at 4 week intervals starting at week 12.
- 200 mg SC LY3074828 Q12W: A dose of 200 mg given as a SC injection at 12 week intervals starting at week 12.

Patients who have clinical responses to placebo (as defined in section 6.11.3.1) at the end of the Induction Dosing Period will continue to receive placebo via SC injection in the Maintenance Dosing period. Placebo responders will not be re-randomized.

Patients who do not have clinical responses to LY3074828 (as defined in section 6.11.3.1) at the end of the Induction Dosing Period will have the option to continue on to the Extension Period-Induction portion of the trial. Patients entering the Extension Period-Induction portion of the trial will not be re-randomized but will receive 1000 mg LY3074828 given as an IV infusion at extension weeks 0, 4, and 8.

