Age, sex and race will be reported on all by-patient listings unless otherwise specified. Sex will be abbreviated as follows: female (F) and male (M). Race will be abbreviated as follows: American Indian or Alaska Native (AI), Asian (AS), Black or African American (BL), Native Hawaiian or other Pacific Islander (NH), White (WH) and Multiple (MU).

There are five study periods defined in section 7.1 of the protocol:

- Screening Period
- Induction Dosing Period

- Maintenance Dosing Period
- Extension Period- Induction
- Extension Period- Maintenance
- Follow Up Period

Table 1 gives the treatment groups to be displayed for each treatment period and analysis population post implementation of protocol amendment (a). NOTE: “LY3074828” will be included in treatment group names in the statistical reports where possible.

Table 1 Treatment Groups for Each Treatment Period and Analysis Population

Treatment Period	Analysis Population	Treatment Groups	Abbreviation	Between Group comparison (when applicable)	Overall Comparison(when applicable)
Induction Dosing Period	ITT, Safety	600 mg LY3074828 IV 200 mg LY3074828 TDM IV 50 mg LY3074828 TDM IV LY3074828 Total Pbo IV	600 mg IV 200 mg TDM IV 50 mg TDM IV LY T total Pbo IV	600 mg IV vs Pbo IV 200 mg TDM IV vs Pbo IV 50 mg TDM IV vs Pbo IV	600 mg IV 200 mg TDM IV 50 mg TDM IV Pbo IV
Maintenance Dosing Period	Induction Responders	200 SC LY3074828 Q4W 200 SC LY3074828 Q12W LY3074828 Total Pbo SC	200 SC Q4W 200 SC Q12W LY T total Pbo SC	200 SC Q4W vs 200 SC Q12W	No Overall Comparison
Extension Period Induction	All enrolled in Extension Period- Induction	600 mg LY3074828 IV 1000 mg LY3074828 IV Total	600 IV 1000 IV Total	600 mg IV vs 1000 mg IV	No Overall Comparison
Extension Period Maintenance	All enrolled in Extension Period- Maintenance	200 mg LY3074828 SC Q4W	200 SC Q4W	No Between-Group Comparison	No Overall Comparison

Note- Patients who received 600mg IV Extension dosing prior to the protocol amendment will be summarized as 600mg IV. Patients who received 1000mg IV Extension dosing after to the protocol amendment will be summarized as 1000mg IV.

Safety summaries will only compare LY Total to Pbo in Induction.

All summary tables will be presented by treatment group. Where applicable, data will be summarized by treatment group by study visit. Summaries and analyses will be presented

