The primary analysis of categorical (binary) efficacy and health outcome variables will use a logistic regression analysis with treatment, geographic region, and prior biologic experience (prior biologic experience vs prior biologic naïve), and visit (when appropriate) in the model. The odds ratio, the corresponding 95% CIs and p-value, as well as the treatment differences (where appropriate) and the corresponding 95% CIs, will be reported. Secondary analysis will be conducted using an exact Cochran-Mantel-Haenszel test that stratifies by (i.e., controls for) previous biologic use. A Fisher's exact test may be utilized if necessary.

The primary analyses for all continuous efficacy and health outcome variables will be based on the MMRM analysis method. The MMRM analyses will be conducted using a restricted maximum likelihood (REML)-based repeated measures approach. When MMRM is used, the model will include treatment, visit, geographic region, prior biologic experience (prior biologic

experience vs prior biologic naïve), treatment-by-visit interaction, as well as the continuous, fixed covariates of baseline value and baseline value-by-visit interaction. The covariance structure to model the within-patient errors will be unstructured. If the unstructured covariance matrix results in a lack of convergence, the heterogeneous Toeplitz covariance structure, followed by the heterogeneous autoregressive covariance structure, followed by the compound symmetry structure will be used. The first structure to yield convergence will be used for inference. The Newton-Raphson with ridging optimization technique will be used to aid with convergence. The Kenward-Roger approximation will be used to estimate the denominator degrees of freedom and adjust standard errors. Type III tests for the LS means will be used for the statistical comparison; the 95% CI will also be reported. Treatment group comparisons with placebo at Week 12 (Visit 7) and all other appropriate time points will be tested.

Secondary treatment comparisons of continuous efficacy variables at Week 12 and 52 will be made using ANCOVA with treatment, geographic region, prior biologic experience (prior biologic experience vs prior biologic naïve), and baseline value in the model. Type III sums of squares for the least-squares (LS) means will be used for the statistical comparison; the 95% confidence interval will also be reported.

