6.2. Analysis Populations

The patient populations to be analyzed for this study are defined in the table presented below:

Table 2 Analysis Populations

Population	Definition
Screening	All patients who signed informed consent and participated in the screening period (Visit 1). This population will be used for the presentation of patient disposition.
Intent-to-Treat (ITT) Population	Efficacy and health outcome analyses will be conducted on the intent-to-treat population (ITT). The ITT population is defined as all randomized patients, even if the patient does not take the assigned treatment, does not receive the correct treatment, or otherwise does not follow the protocol. Patients will be analyzed according to the treatment to which they were assigned.
Safety Population	Safety analyses will be conducted on the Safety Population, defined as all randomized patients who receive at least one dose of study treatment. Patients will be analyzed according to the treatment to which they were assigned.

Induction Responders	A subset of the ITT population and will include those patients who are re-randomized to one of the two maintenance dosing period LY arms.
All enrolled in Extension Period	A subset of the ITT population and will include only the patients who participated in the Extension Period.

Analyses of the maintenance dosing period and the extension periods will be based on the corresponding enrolled population as described in the table above.

The Schedule of Events outlined in the protocol (attachment 1) specifies the allowable windows for assessments. A sensitivity analysis of the primary analysis may be conducted to investigate the exclusion of patients /assessments deemed to be major deviations from the protocol.

A Per-Protocol population may be evaluated in this study and patients to be excluded from that population will be identified through protocol deviations. All protocol exemptions and violations will be listed as described in section 9.10 of the protocol.

All statistical analyses will be performed using SAS software Version 9.2 (or a higher version). Visualizations tools such as Spotfire may also be used for dynamic displays.

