6.3. Adjustments for Covariates

The randomization at the beginning of the Induction Period is stratified by previous biologic therapy: previous exposure to biologic therapy for treatment of UC, biologic naïve to biologic therapy for treatment of UC. Unless otherwise specified, all efficacy and health outcome analyses will include the stratification factors in the model.

The re-randomization at the beginning of the Maintenance Period of patients who took LY3074828 during the Induction Period and were responders at Week 12 (Visit 7) is stratified by the Week 12 level of clinical response: Clinical Remission or Clinical Response. Unless otherwise specified, all efficacy and health outcomes analyses using the Maintenance Dosing Period Primary population will include the re-randomization factor of Week 12 level of response in the model.

Unless otherwise specified, analyses will be performed utilizing the methodology and covariates described in section 6.1.

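### SAP 6.14.9 tests Week 52 histology scores against a placebo group that is not a randomised comparator and that SAP Table 1 does not list; at Week 12 the same t-test is valid but gives up precision

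*SAP*

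**What the plan says.** **The test.** SAP 6.14.9 on the histology scores: "Two sample unpaired t-test will be employed to analyze the mean difference at Week 12 and Week 52 between each active treatment arm and placebo". It names no covariates, does not say whether the test is on the score or the change, and does not say which active arms are meant at Week 52. Histologic remission at Weeks 12 and 52 is instead sent to the methods of SAP 6.1, without naming the contrast.

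**The general method.** SAP 6.1 makes MMRM primary for continuous efficacy variables, then adds: "Secondary treatment comparisons of continuous efficacy variables at Week 12 and 52 will be made using ANCOVA with treatment, geographic region". That model also includes prior biologic experience and the baseline value.

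**Who has a Week 52 biopsy.** In Protocol Attachment 1, biopsies are scheduled at screening, at Visit 7 and at Week 52 of maintenance. On entry to maintenance, SAP 5.1 says: "Patients defined as having clinical responses at Week 12 will continue study participation in the maintenance period up to Week 104". SAP 5.3 re-randomises LY3074828 (LY) responders to Q4W or Q12W and adds: "Placebo responders will not be re-randomized".

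**Planned maintenance comparisons.** SAP Table 1 lists one: "200 SC Q4W vs 200 SC Q12W". SAP Table 2 defines the Induction Responders as "those patients who are re-randomized to one of the two maintenance dosing period LY arms". SAP 6.3 says maintenance efficacy analyses "will include the re-randomization factor of Week 12 level of response in the model".

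**Protocol against SAP.** Protocol 12.2.6.2 tests each treatment arm against placebo by logistic regression for endpoints that include Week 52 endoscopic remission and the three Week 52 durability measures. SAP Table 3 defines durability only among patients who had the same status at Week 12. SAP 6.18 does not mention dropping a placebo comparison and states that nothing further has changed from the protocol.

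**The concern.** Week 12 response is itself affected by treatment. Placebo responders improved without the drug. LY responders are a mixture of patients who would have improved anyway and patients who improved because of the drug. A Week 52 score difference between these groups can therefore reflect case mix as well as any drug effect, and a t-test cannot separate the two. Baseline adjustment would not restore randomisation either.

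The analyst also receives conflicting instructions, because 6.14.9 orders a placebo test in a period for which Table 1 lists none. The same question arises for Week 52 histologic remission, since 6.1 supplies a model but not a valid comparator. It arises again for the Week 52 endpoints in Protocol 12.2.6.2. A reader of the report could take any of these p-values as randomised evidence of a maintained effect.

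At Week 12 only precision is at stake. A baseline biopsy is already collected and the t-test does not use it.

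**Working it through.** **The plan's own figure.** Inputs from Protocol 12.1 and SAP 5.2: 60 per arm, remission 30% against 7.5%, two-sided 0.05. Pooled chi-square: z = (0.225 × √60 − 1.96 × √(2 × 0.1875 × 0.8125)) / √(0.30 × 0.70 + 0.075 × 0.925) = (1.743 − 1.082) / 0.529 = 1.25, so power is 89.4%. The stated 89% is reproduced. The plan states no figure for histology or for Week 52.

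**Week 12: precision.** Let ρ be the correlation between baseline and Week 12 score. The documents do not give it; 0.3 to 0.6 is assumed, with scores for 60 per arm. The variance of the t-test relative to ANCOVA is 1/(1 − ρ²) on the raw score and 2/(1 + ρ) on the change. The equivalent ANCOVA sample size is 60 divided by that ratio.

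| ρ | Raw score: ratio | Equivalent n per arm | Change: ratio | Equivalent n per arm |
|---|---|---|---|---|
| 0 | 1.00 | 60 | 2.00 | 30 |
| 0.3 | 1.10 | 54.6 | 1.54 | 39 |
| 0.5 | 1.33 | 45 | 1.33 | 45 |
| 0.6 | 1.56 | 38.4 | 1.25 | 48 |

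For an assumed effect of 0.5 SD, power is 78% with the t-test on the raw score and 82% to 93% with ANCOVA over ρ = 0.3 to 0.6.

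**Week 52: who is compared.**
1. A main-study Week 52 biopsy requires entry to maintenance, and entry requires Week 12 response.
2. LY responders are re-randomised between two LY regimens. Protocol 7.2 rules out allocating any LY-treated subject to maintenance placebo.
3. The placebo group is therefore the placebo responders, left on placebo without re-randomisation.
4. Reading the active arms as the original induction arms does not help, because the same response filter applies to each of them.
5. The extension biopsy at Extension Week 40, about study Week 52, does not help either. Extension nonresponders leave at Extension Visit 6 (Protocol 7.1.1), and nobody in the extension receives placebo (Protocol 7.2).

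The only randomised maintenance contrast is Q4W against Q12W.

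**Week 52: illustrative numbers.** Response rates are assumed: 20–35% on placebo and 50–60% on LY.
- Placebo responders: 60 × 0.20 to 0.35 = 12 to 21.
- LY responders per maintenance arm: 180 × 0.50 to 0.60 / 2 = 45 to 54.
- If everyone who responds on placebo would also respond on LY, the drug-induced share of LY responders is 1 − (placebo rate / LY rate). This runs from 1 − 35/50 = 0.30 to 1 − 20/60 = 0.67.

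Each 1-point RHI difference at Week 52 between the two kinds of responder would then shift the comparison by 0.3 to 0.7 point, in either direction. This is a conversion factor, not an estimate of bias. The shift is zero if the two kinds fare equally, or if LY induces no extra responses.

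**The case against.** **Week 12 is a matter of preference.** The t-test is valid, SAP 6.3 allows a section to specify otherwise, and 6.14.9 sits under safety analyses. That is correct as far as it goes: this is a departure from the default and not a breach. A reader might infer that the Week 12 result is biased, and the documents do not support that. Precision is still lost at no saving. SAP 6.1 does make MMRM primary and ANCOVA secondary, but induction has a single post-baseline biopsy visit, so ANCOVA is the natural form.

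**Table 1 is only general.** Its comparison column is headed as applying where applicable, and it displays a placebo SC group in maintenance. A specific section might be held to override it. Displaying a group is not comparing it, however, and overriding Table 1 would not make the contrast randomised.

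**The Week 52 bias is not demonstrated.** This stands. A reader might infer that the test favours LY, or works against it. The documents fix neither size nor direction, and every rate used above for Week 52 is assumed.

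**Durability.** A reader might infer that the protocol's durability test is hopelessly underpowered. The planned rates give 60 × 0.075 = 4.5 expected placebo remitters against 180 × 0.30 / 2 = 27 per maintenance arm. Averaged over the distribution of placebo remitters, Fisher power for an assumed 30-point gain (30 to 60%, 40 to 70% or 50 to 80%) is 13–20%. But that combines the protocol's placebo test with the SAP's conditional definition and the SAP's maintenance arms. The protocol sets ITT as its default and does not restrict the denominator. Counting remission at both visits out of all 60 per original arm is a randomised contrast, though a different estimand, and the same assumed rates give Fisher power of 78–89%. The figure depends on the reading, so no power conclusion is drawn.

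**SAP 6.18 is not the only record.** SAP 6.1 lets non-principal changes be described in the study report. That is true, but the closing statement in 6.18 remains inaccurate if the placebo comparison has been dropped.

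**Conclusion.** The Week 52 score test against placebo should not stand. It is not a randomised comparison and it conflicts with Table 1. Both conclusions follow from the documents without any assumption. Week 52 histologic remission would have the same problem if the 6.1 model were run against placebo.

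The Week 12 point is smaller: 1.10 to 1.56 times the ANCOVA variance on the raw score, or 1.54 to 1.25 times on the change, for an assumed correlation of 0.3 to 0.6. On the raw score the loss is nil at zero correlation.

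For Week 52 endoscopic remission and durability, the finding is an undeclared difference between protocol and SAP that needs reconciling. It is not a demonstrated error in either definition.

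All of this concerns secondary or exploratory analyses. The Week 12 primary endpoint and its testing sequence are untouched. The point should be fixed but does not threaten the trial's main conclusion.

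**What to change.** 1. **SAP 6.14.9, Week 12.** Replace the t-test with the SAP 6.1 ANCOVA, including baseline score, prior biologic experience and region.
2. **SAP 6.14.9, Week 52.** Delete the score test against placebo. Compare Q4W with Q12W in the Induction Responders, adjusting for Week 12 remission status as in SAP 6.3. Apply the same restriction to Week 52 histologic remission. Show placebo responders descriptively. Selecting on Week 12 response is harmless for Q4W against Q12W because it precedes the re-randomisation.
3. **Protocol 12.2.6.2 and SAP Tables 1–3.** State which Week 52 comparisons with placebo, if any, will be made for endoscopic remission and the durability measures, and in which population. Correct the closing statement of SAP 6.18 to match.

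The cost is SAP wording and minor programming. The covariates are already collected, and no patient or visit is added. The downside is that there will be no formal Week 52 p-value against placebo for histology.
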